CGM Group: Patients will wear a real-time Dexcom G6 CGM, which provide BG readings every 5 minutes for up to 10 days. In addition, patients will undergo POC testing before meals and bedtime per hospital protocol. Insulin therapy will be titrated based on daily CGM printouts, which will include BG readings, glycemic excursions, hypoglycemia and severe hyperglycemia values throughout the day. Patients will wear a CGM in the current approved insertion site, the abdomen, and in the upper arm, both during hospitalization (up to 10 days).

Primary and Secondary Research Outcomes:

The primary aim is difference between POC testing (standard of care) and CGM in glycemic control (efficacy outcome) and hypoglycemic events (safety outcome) during hospitalization:

- 1) Glycemic control, as measured by time in range between 80-180 mg/dl (efficacy outcome)
- 2) Clinically significant hypoglycemia <54 mg/dl (safety outcome)

Secondary outcomes include differences between groups in any of the following measures:

1. Nocturnal hypoglycemia < 70 mg/dl and < 54 mg/dl (between 22:00 and 06:00)
2. Number of hypoglycemia events (< 70 and 54 mg/dl)
3. Duration or time in hypoglycemia (minutes) during the day and night
4. Frequency and duration of time in hyperglycemia > 250 mg/dl
5. Percentage of BG readings within target BG of 80 and 180 mg/dl
6. Glycemic variability calculated by Standard Deviation, and MAGE
7. Differences in BG by CGM devices placed in the abdomen and upper extremity
8. Number of sensor removal for procedures/imaging, sensors failures, sensors dislodgments

9. After discharge: time in range (TIR), frequency of and time in hypoglycemia (TIHypo), frequency of and time in hyperglycemia (TIHyper), glycemic variability (GV)

Inclusion Criteria:

1. Males and females \geq 18 years admitted to a general medicine or surgical services.
2. Diagnosis of: T1D or T2D receiving insulin therapy during hospital admission.
3. Subjects must have a randomization BG $<$ 400 mg/dL without laboratory evidence of diabetic ketoacidosis (bicarbonate $<$ 18 mEq/L, pH $<$ 7.30, or positive serum or urinary ketones).
4. Patients with expected hospital length-of-stay of 2 or more days

Exclusion Criteria:

1. Patients with acute illness admitted to the ICU or expected to require admission to the ICU.
2. Patients expected to require MRI procedures during hospitalization.

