- Subjects treated with insulin prior to admission will receive 80% of the total daily dose (TDD) given as basal bolus regimen with basal insulin (glargine, detemir or degludec) once daily plus rapid-acting insulin (lispro or aspart) before meals.
- Half of TDD will be given as basal and half as rapid-acting insulin.
- Basal insulin will be given once daily, at the same time of the day.
- Rapid-acting insulin will be given in three equally divided doses before each meal. To prevent hypoglycemia, if a subject is not able to eat, prandial insulin will be held.

Insulin Naïve T2D Patients Treated with Oral Agents or GLP1-RA Prior to Admission

- Discontinue oral antidiabetic drugs on admission.
- Starting total daily insulin dose:
 - 0.4 U/Kg/day when randomization BG between 140-200 mg/dL
 - 0.5 U/Kg/day when randomization BG between 201-400 mg/dL
 - 0.5 U/Kg/day if HbA1C: 7.5% to 8.4%
 - 0.6 U/Kg/day for HbA1C $\geq 8.5\%$
 - Reduce TDD to 0.3 units per kg in patients ≥ 70 years of age and/or with an eGFR $< 60\text{ ml/min}$.
- Half of TDD will be given as basal insulin (glargine, detemir or degludec) once daily plus rapid-acting insulin (lispro or aspart) before meals.
- Basal insulin will be given once daily, at the same time of the day.
- Rapid-acting insulin will be given in three equally divided doses before each meal. To prevent hypoglycemia, if a subject is not able to eat, prandial insulin dose will be held.

To make daily insulin adjustments, POCT BG values will be used in the standard of care group. For those in the CGM group, the previous 24 hour glucose profile will be used to adjust insulin. The following guidelines will be used for insulin adjustment, at the physician discretion:

- Fasting glucose will be defined as average BG from 00:00 – 06:00AM. Basal insulin will be adjusted based on this level.

- Prandial adjustments – increase in dose is recommended if peak BG within 4 hours after a meal is >180mg/dL.

Basal Insulin adjustment.

- Daily basal (glargine, detemir or degludec) insulin dose will be adjusted as follow:
 - If the fasting and pre-dinner BG is between 100 - 140 mg/dl in the absence of hypoglycemia the previous day: no change
 - If the fasting and pre-dinner BG is between 141 - 200 mg/dl in the absence of hypoglycemia: increase basal insulin by 10% every day
 - If the fasting and pre-dinner BG is between 201 - 280 mg/dl in the absence of hypoglycemia: increase basal insulin by 20% every day

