Use of CGM. No major risks are expected with the use of the CGM device. Pain and bleeding with insertion is minimal. Skin irritation may occur in those sensitive to adhesives. Other potential risks and drawbacks of using CGM described in the literature including unrealistic expectations and overly aggressive correction of elevated glucose levels. Patients will be protected from this after discharge as all discharge CGMs will be blinded with insulin adjustments being made based on POC BG standard of care.

Protection against Risks

We will follow safeguards to minimize the risk to our subjects: a) we will carefully monitor capillary BG at the bedside using a hand-held glucose meter, b) only experienced nurses/or phlebotomist will draw blood samples, and c) women of reproductive age who are sexually active will undergo a urine pregnancy tests prior to participation in the study. To prevent significant clinical events, no patients with history of significant liver, renal impairment or cardiac failure will be recruited in this study.

We expect that approximately 10% in the inpatient setting and ~20% in the outpatient (post-discharge) arm will experience one or more episodes of hypoglycemia. To minimize the risk of hypoglycemia, the starting dose will be reduced in the basal bolus insulin regimen (TDD: 0.4 units per kg of body weight), in addition, in patients \geq 70 years of age and/or eGFR < 60 ml/min the TTD will be further reduced to 0.3 units/kg. To avoid hypoglycemia, the total daily dose of insulin will be decreased by 10% for BG between 70-99 mg/dl and by 20% after each episode of hypoglycemia (BG < 70 mg/dl). In addition, in patients treated with insulin at home, the TDD of insulin will be reduced by 20% on admission and the attending physician may further reduce insulin dose in the presence of severe hypoglycemia.

CGM – alarms and hypoglycemia protocol. We will use a Dexcom CGM "blinded" device with a modified transmitter able to store and transmit glucose data to different devices including a notebook/IPAD or computer desk located at the nursing station. **The use of hypoglycemia alarm** set at 80 mg/dl will alert nursing staff and

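### Starting insulin doses for insulin-naive T2D patients overlap without a rule of precedence, conflict with the 0.4 U/kg in the safety section, and leave one eligible group with no dose

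*Combined protocol and SAP*

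**What the plan says.** Section III, Recommended Basal Bolus Insulin Protocol, has a list of starting total daily doses for insulin-naive T2D patients previously on oral agents or GLP1-RA. Two rows depend on randomization glucose: "0.4 U/Kg/day when randomization BG between 140-200 mg/dL" and "0.5 U/Kg/day when randomization BG between 201-400 mg/dL". Two depend on HbA1c: "0.5 U/Kg/day if HbA1C: 7.5% to 8.4"%, and "0.6 U/Kg/day for HbA1C" of 8.5% or more. A fifth row is an override: "Reduce TDD to 0.3 units per kg in patients" aged 70 or over and/or with eGFR below 60 ml/min. Nothing links the glucose rows to the HbA1c rows.

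Earlier in the same section, the protocol says that first-day dosing starts from POC glucose values in both groups. HbA1c is not mentioned there.

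Section V, Protection against Risks, lists among the measures against hypoglycemia that "the starting dose will be reduced in the basal bolus insulin regimen (TDD: 0.4 units per kg of body weight"), with a further reduction to 0.3 for the same age and eGFR group. No glucose or HbA1c condition is attached to the 0.4.

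The third inclusion criterion, which begins "Subjects must have a randomization BG", sets an upper limit of 400 mg/dl and no lower limit.

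**The concern.** A starting-dose rule should give each eligible patient one dose. Here a patient has both a glucose and an HbA1c, the two sets of rows sit side by side, and they need not agree. Two clinicians following the text faithfully could start the same patient on different doses. The safety section then describes a single starting dose, offered as a safeguard, that is lower than three of the four rows in the treatment section.

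At stake is the safety of the patients concerned, because the starting dose bears on early hypoglycemia and hypoglycemia below 54 mg/dl is the trial's safety outcome. Dosing may also vary by clinician or site, unrelated to the monitoring method under test.

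**Working it through.** The plan states no derived figure to reproduce. The check crosses the dose rows and lists every dose that applies to one patient.

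**Inputs (U/kg/day).** Section III: glucose 140-200 mg/dl, 0.4; glucose 201-400, 0.5; HbA1c 7.5-8.4%, 0.5; HbA1c 8.5% or more, 0.6; no HbA1c row below 7.5%; no glucose row below 140. Section V: 0.4, unconditional. Patients aged 70 or over and/or with eGFR below 60 are left out, because the 0.3 rule overrides the rows for them and is the same in both sections.

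**Formula.** Ratio = highest applicable dose / lowest applicable dose, first within Section III, then with the 0.4 of Section V added.

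| Glucose (mg/dl) | HbA1c | Section III doses | Ratio | Ratio with Section V |
|---|---|---|---|---|
| 140-200 | <7.5% | 0.4 | 1.00 | 1.00 |
| 140-200 | 7.5-8.4% | 0.4, 0.5 | 0.5/0.4 = 1.25 | 1.25 |
| 140-200 | ≥8.5% | 0.4, 0.6 | 0.6/0.4 = 1.50 | 1.50 |
| 201-400 | <7.5% | 0.5 | 1.00 | 0.5/0.4 = 1.25 |
| 201-400 | 7.5-8.4% | 0.5, 0.5 | 1.00 | 0.5/0.4 = 1.25 |
| 201-400 | ≥8.5% | 0.5, 0.6 | 0.6/0.5 = 1.20 | 0.6/0.4 = 1.50 |
| <140 | <7.5% | none | - | - |
| <140 | 7.5-8.4% | 0.5 | 1.00 | 0.5/0.4 = 1.25 |
| <140 | ≥8.5% | 0.6 | 1.00 | 0.6/0.4 = 1.50 |

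**Results.**

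1. Of the four combinations in which a glucose row and an HbA1c row both apply, three conflict within Section III (+50%, +25%, +20%). The fourth, glucose 201-400 with HbA1c 7.5-8.4%, gives 0.5 both ways.
2. Against Section V, every combination that can lead to 0.5 or 0.6 conflicts with 0.4.
3. Glucose below 140 with HbA1c below 7.5% has no starting-dose row in Section III.

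**In units.** The documents give no body weight. At an assumed 80 kg, 0.4, 0.5 and 0.6 U/kg give 32, 40 and 48 U/day. The widest gap is 0.2 U/kg, so 14 U/day at 70 kg, 16 at 80 kg and 20 at 100 kg.

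**Persistence.** Daily titration moves doses by percentages. Two of the 20% reductions prescribed after glucose below 70 mg/dl take 0.6 to 0.6 × 0.8 × 0.8 = 0.384. In the other direction, the basal half of the dose starts at 0.2 or 0.3 U/kg. Starting from 0.2, five 10% steps (0.2 × 1.1^5 = 0.322) or three 20% steps (0.2 × 1.2^3 = 0.346) are needed to reach 0.3. The expected stay is at least 2 days in the inclusion criteria and more than 3 in the design text. A difference in starting dose can therefore last beyond the first day, though the documents do not allow an estimate of its effect.

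**The case against.** The strongest reply on precedence is the sentence that POC glucose starts dosing on the first day, which could be read as putting the glucose rows first. That sentence names the glucose source for both groups (POC rather than CGM) and is silent on HbA1c. Read as a precedence rule, it would leave the HbA1c rows without a use, and 0.5 for glucose 201-400 would still conflict with the 0.4 in Section V. The heading does call the regimen recommended, but for T2D the discretion given to physicians is attached to dose adjustment, not to the starting dose.

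Other objections stand and limit the point:

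- A reader might infer that most patients are affected. The documents give no distribution of glucose or HbA1c and no count of insulin-naive patients. T1D patients and T2D patients already on insulin follow other rules, and the 0.3 override removes the older and renally impaired.
- A reader might infer that the Section V safeguards as a whole differ from the treatment protocol, or that the ethics board sees only the safety version. Neither is supported. The 0.3 rule, the 20% cut for home-insulin users, the 10% cut at 70-99 mg/dl and the 20% cut below 70 all agree between sections. The whole protocol goes to the board.
- A reader might infer that any patient with glucose below 140 has no dose. With HbA1c of 7.5% or more, an HbA1c row still applies.
- A reader might infer bias in the treatment comparison. The starting rules are the same in both arms, and Section IV confines the analysis to hospital glucose values after the first day of insulin treatment.

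**Conclusion.** The contradiction is real and can be shown from the text alone. It covers insulin-naive T2D patients under 70 with eGFR of at least 60. Within Section III the same patient can fit doses that differ by 50%, 25% or 20%, depending on the combination. The 0.4 U/kg in Section V also conflicts with the 0.5 and 0.6 rows. In this group, glucose below 140 with HbA1c below 7.5% is eligible but fits no row.

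The percentages rest only on the stated doses; the figures in units assume a body weight. The number of patients affected and the effect on hypoglycemia or mean glucose cannot be estimated from the documents. No bias between arms is shown. The point is worth correcting because it concerns a starting insulin dose and a stated protection against hypoglycemia.

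**What to change.** The clinical team should reconcile the starting-dose list and the first-day POC glucose sentence in Section III with the starting dose in Section V. The result should be one non-overlapping rule that says how glucose and HbA1c are used together and that covers every eligible patient, including those with glucose below 140 mg/dl and HbA1c below 7.5%. The same rule should then appear identically in the treatment and safety sections. Which dose is right, and whether glucose or HbA1c should take precedence, are clinical decisions on which no view is given here.

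The cost is a protocol wording amendment. No extra patients, visits or measurements are needed.

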****Check appropriate column and cross out other columns**

*BG (mg/dL)	 Insulin Sensitive	 Usual	 Insulin Resistant
< 141	No sliding scale (supplemental)insulin		
141 – 180	2	3	4
181 – 220	3	4	6
221 – 260	4	5	8
261 – 300	5	6	10
301 – 350	6	8	12
351 – 400	7	10	14
> 400	8	12	16

BEDTIME sliding scale: Supplemental Sliding Scale Insulin dose at bedtime starting at BG > 220 mg/dL

*BG (mg/dL)	 Insulin Sensitive	 Usual	 Insulin Resistant
< 220	No sliding scale (supplemental) insulin		
221 – 260	1	2	4
261 – 300	2	3	5
301 – 350	3	4	6
351 – 400	4	5	7
> 400	5	6	8

*BG by POCT will be used in the standard of care group and CGM values at time of insulin administration will be used for those in the Dexcom CGM group.

Hospital Diabetes Education.

1. Diabetes education if not received within 1 year of admission
2. Use of glucose meters for home glucose self-monitoring
3. Keeping BG records, and will receive a logbook to record glucose tests results
4. Training on placement and care of CGM Dexcom G6
5. Hypoglycemia prevention, recognition and management

Aim 2. To examine differences in glycemic control after hospital discharge between Dexcom G6 CGM and POC BG testing in hospitalized patients with T1D and T2D.

During the hospital stay, patients will be instructed on CGM placement and care. The CGM system training sessions will be performed by a diabetes educator. The diabetes educator will educate patients on how CGM system differs from capillary SMBG, reinforcing the need for continued SMBG. Patients interested in participating in the study and willing to and able to use the CGM device will be recruited. A new CGM (blinded) will be placed prior to discharge. Patients will be asked to return for a clinic visit after 10 days of discharge (sooner or later depending on participant's schedule). Downloading of the sensors will be performed at the day of discharge and during follow up visit after hospital discharge.

Insulin Discharge Algorithm¹²:

Patients will be discharged following a standard protocol taking in consideration preadmission treatment (oral agents or insulin) and HbA1c value on admission as previously reported ¹².

Patients with poorly controlled diabetes (HbA1c >7.5%) enrolled in Aim 1 will be invited to participate in this open label prospective outpatient study. The total duration of the study is 10 days.

- Patients with admission HbA1c < 7.5% will be discharged on their preadmission antidiabetic regimen.
- Patients on oral agents prior to admission with an HbA1c between 7.5% and <10% will be discharged on oral agents plus basal insulin (glargine, detemir, degludec) at 50% of the daily hospital dose.
- Patients on oral agents prior to admission with an admission A1C ≥ 10% will be discharged on their oral agents plus basal insulin at 80% of daily hospital dose.
- Patients on oral agents plus basal insulin (NPH, glargine, detemir) prior to admission with an admission A1C between 7.5% and <10% will be discharged on their oral agents plus basal insulin at 50% of daily hospital dose.
- Patients on oral agents plus basal insulin (NPH, glargine, detemir) prior to admission with an admission A1C ≥ 10% will be discharged on their oral agents plus basal insulin at 80% of daily hospital dose.
- Patients treated with basal bolus regimen prior to admission will be discharged on 80% of their preadmission TDD with basal insulin once daily and rapid-acting insulin before meals.

Follow-up Care:

- Duration of post discharge study: ~10 days (participant can return sooner or later depending on his/her schedule)
- New CGM (blinded) sensor will be placed (abdomen or arm at investigator's discretion) before discharge. If primary care team is planning to discharge over the weekend: participants will get new blinded sensor on Friday evening prior to discharge. The real time CGM will be left in the abdomen to continue to monitor during hospital stay. Participant will be asked to return on the following business working day to remove real time CGM. Blinded sensor (placed before discharge) will be removed at 10 day follow up visit after discharge.
- Patients will be asked to continue checking their blood glucose by regular POCT and will return to the outpatient clinic visit at 10 days after discharge (sooner or later depending on participant's availability and schedule).

The following information will be collected after discharge:

1. Glycemic control:
 - a. Mean daily blood glucose by CGM and POC testing
 - b. Time in range (80-180 mg/dl)
 - c. Frequency of overall clinically significant hypoglycemia (<54 mg/dl) and severe hyperglycemia (>250 mg/dl).
 - d. Nocturnal hypoglycemia < 70 mg/dl and < 54 mg/dl (between 22:00 and 06:00)
 - e. Duration or time in hypoglycemia (minutes) during the day and night
 - f. Frequency and duration of time in hyperglycemia > 240 mg/dl
 - g. Percentage of BG readings within target BG of 80 and 180 mg/dl (time in range)
 - h. Glycemic variability calculated by Standard Deviation, and MAGE
2. Diabetes treatment:
 - a. Number of patients receiving insulin
 - b. Insulin dosage (unit/day)
 - c. Use of oral agents
3. Clinical Outcome:
 - a. Hospital readmissions
 - b. Emergency room visits

Study Sites:

The study will be conducted in three academic institutions: Grady Memorial Hospital ([name] and [name]), Midtown Emory Hospital ([name]), and at the University of Maryland and VA Maryland Health Care System (PI: [name]).

IV. Statistical Methods

The present study is one of two projects aimed to investigate the role of CGM (Dexcom G6 CGM) in the management of patients with diabetes in non-ICU setting receiving basal bolus insulin treatment. These prospective studies will explore the efficacy of CGM compared to standard POC glucose testing in assessing glucose control (efficacy) and hypoglycemic events (safety) as well as in guiding insulin therapy in patients with diabetes during admission and after hospital discharge. [name], PhD at the School of Public Health at Emory University will conduct statistical analyses.

The primary efficacy endpoint is glycemic control measured by mean daily BG concentration and time in range between patients managed by POC testing (standard of care) and CGM. To show non-inferiority between POC and CGM in terms of glycemic control, we set the equivalence margin of 18 mg/dl (1 mOsm/l), from a view that a difference <18 mg/dl is usually not considered as clinically significant (12, 14, 16). Based on the results

from Rabbit medicine and surgery trials, it is reasonable to assume the standard deviation of mean daily BG is bounded above by 45 mg/dl. Assuming the true BG difference between the treatment groups is zero, and using one-sided, two-sample t-tests, we require 78 subjects for each treatment group to achieve 80% power. Accounting for 10% attrition rate, we would need 90 patients per treatment group, which means 180 subjects in total, to achieve >80% power in Aim 1.

We will report baseline characteristics by hospital service (medicine and surgery), diabetes type, and risk factors for hypoglycemia. The rates of incidence of hypoglycemia will be calculated based on the data obtained by CGM and POC. Comparisons will be made with the use of Wilcoxon tests (or Kruskal-Wallis tests) and Chi-square tests (or Fisher's exact test) as appropriate. Multivariate linear regression will be conducted to assess the difference in continuous secondary outcomes between the two groups while other relevant covariates. To be eligible for analysis at least 70% of CGM values need to be available per day, with at least 2 eligible days of data per subject in each study arm (inpatient and outpatient). Glucose patterns will be analyzed based on the Ambulatory Glucose Profile, recently endorsed by an international expert as a standardized approach for CGM interpretation⁴⁴. Hospital glucose values after the first day of insulin treatment will be included in the analysis to allow us to have a full 24-hrs glucose profile and to avoid analyzing day-1 CGM values which may have lower accuracy. For clinical accuracy, CGM and POC BG will be paired and will be plotted in the Clarke Error Grid^{46,47}. Paired CGM and POC BG falling in the Zone A will be defined as "accurate", and in Zone B as "acceptable", with remaining values considered "not acceptable" if falling in Zone C, D, or E.

A total of 180 insulin treated patients will be included in this prospective study. Based on previous studies by our unit, we anticipate that 80% of patients will complete the inpatient and ambulatory arms of the study^{13,48}.

V. Methods and Procedures Applied to Human Subjects:

Potential Risk to Human Subjects

Hypoglycemia. The risk of hypoglycemia in non-ICU patients treated with basal-bolus insulin is between 12%–35%^{14,19,37,49}. In this analysis, hypoglycemia is defined as a BG or IG < 70 mg/dL. Clinical significant hypoglycemia is defined as BG or IG < 56 mg/dL. Severe hypoglycemia is defined as BG or IG < 40 mg/dL.

Use of CGM. No major risks are expected with the use of the CGM device. Pain and bleeding with insertion is minimal. Skin irritation may occur in those sensitive to adhesives. Other potential risks and drawbacks of using CGM described in the literature including unrealistic expectations and overly aggressive correction of elevated glucose levels. Patients will be protected from this after discharge as all discharge CGMs will be blinded with insulin adjustments being made based on POC BG standard of care.

Protection against Risks

We will follow safeguards to minimize the risk to our subjects: a) we will carefully monitor capillary BG at the bedside using a hand-held glucose meter, b) only experienced nurses/or phlebotomist will draw blood samples, and c) women of reproductive age who are sexually active will undergo a urine pregnancy tests prior to participation in the study. To prevent significant clinical events, no patients with history of significant liver, renal impairment or cardiac failure will be recruited in this study.

We expect that approximately 10% in the inpatient setting and ~20% in the outpatient (post-discharge) arm will experience one or more episodes of hypoglycemia. To minimize the risk of hypoglycemia, the starting dose will be reduced in the basal bolus insulin regimen (TDD: 0.4 units per kg of body weight), in addition, in patients \geq 70 years of age and/or eGFR < 60 ml/min the TTD will be further reduced to 0.3 units/kg. To avoid hypoglycemia, the total daily dose of insulin will be decreased by 10% for BG between 70-99 mg/dl and by 20% after each episode of hypoglycemia (BG < 70 mg/dl). In addition, in patients treated with insulin at home, the TDD of insulin will be reduced by 20% on admission and the attending physician may further reduce insulin dose in the presence of severe hypoglycemia.

CGM – alarms and hypoglycemia protocol. We will use a Dexcom CGM "blinded" device with a modified transmitter able to store and transmit glucose data to different devices including a notebook/IPAD or computer desk located at the nursing station. **The use of hypoglycemia alarm** set at 80 mg/dl will alert nursing staff and

providers that a patient maybe at risk of hypoglycemia. If this occurs, the nursing staff will meet patient in the room to assess clinical status and signs/symptoms of hypoglycemia and will perform a POC glucose testing. A carbohydrate load of 15 grams will be provided to patients to avoid clinically significant hypoglycemia.

Clinically significant hypoglycemia defined as POC <80 will be treated per hospital protocol in both groups.

Nursing staff should perform a POCT BG if the patient complains of symptoms of hypoglycemia, even in the absence of CGM alarms. POCT BG should be treated accordingly.

Insertion of the CGM sensor will be performed per manufacturer instructions and following an aseptic technique. After insertion of the sensors, providers will ensure proper hemostasis is achieved. Sensors will be removed if prolonged bleeding or severe pain occurs.

Recruitment and Consent. Coordinators will screen for potential participants from the electronic medical record. Subjects will be provided with sufficient information on the practice of glucose monitoring before providing written consent. The process of obtaining informed consent will follow the standard procedures of Emory University. This protocol will be submitted for approval by the Emory IRB.

Potential Benefits to Human Subjects. Subject participating in this trial will not receive any direct benefits during the hospital stay, since treatment decision will be made based on POC BG (standard of care). In the outpatient arm, investigators will analyze glucose profiles in a more detailed manner with potential for better treatment modifications.

Inclusion of children. No patients under the age of 18 will be recruited in this study.

Confidentiality. Informed consent will follow the procedure of Emory University Institutional Review Board. Every potential participant will be informed in writing and verbally with the important and key points of the study. One of the investigators or research coordinators will obtain a witnessed informed consent prior to inclusion of a patient into the study. Data collection records with personal identifiers will be stored in locked file cabinets. Presentation of the study results at regional or scientific meetings or in publications will not identify subjects. Access to research and confidential records will be limited to clinical investigators, coordinators and the IRB at Emory University.

Payment for Participation. Participation in this study is voluntary. Patients will receive one hundred dollars (\$100.00) during the hospital stay, if patient withdraws before discharge, compensation will be provided at \$10 per day during the inpatient stay and no more than \$100. Seventy-five dollars (\$75.00) at the 10 day clinic visit after discharge. Total compensation will be one hundred and seventy-five dollars (\$175.00).

Financial Obligation. No additional cost to patients or to the institution will be incurred for research purposes. Research studies will be performed at no cost to study subjects. CGM will be provided by the sponsor at no cost to participants.

Research Injuries. If a patient is injured because of taking part in this study, [name] and investigators, along with the medical facility will make medical care available to the patient at the patient's own cost. Financial compensation for such things as lost wages, disability or discomfort due to an injury related to the study is not available.

Financial Conflict of Interests. None of the investigators in this study have any outside activities that may represent a conflict of interest. None of the investigators have an economic interest in an outside entity, or act as officers, directors, employees or consultants with such an entity, whose financial interest may be affected by this research study.

Informed Consent. After identification of eligible patients these individuals will be provided basic information regarding the study and, if interested, they will then be screened by research staff using the inclusion/exclusion criteria delineated elsewhere in this protocol. The consent form, potential risks and benefits, and the rights of research participants will be explained to the participant by the investigators or research coordinator. Individuals will be asked if they have any questions, and research staff will answer these questions. The principal investigator will also be available to answer questions that participants may have during the consent procedure or during the time a participant is enrolled in the study. The consent form will be

completed in accordance with the IRB guidelines of Emory University. A signed copy of the consent form will be provided to the participant and a copy will be placed in the file that is maintained for each participant in the study office.

References

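### The trial is sized for a non-inferiority test of mean daily BG, but the analysis paragraph names only difference tests and gives no alpha and no decision rule against the 18 mg/dl margin

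*Combined protocol and SAP*

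**What the plan says.** All the relevant text stands under the single heading IV, Statistical Methods.

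- **Objective and margin:** "To show non-inferiority between POC and CGM in terms of glycemic control, we set the equivalence margin of 18 mg/dl". The endpoint sentence just before it names mean daily BG and time in range together.
- **Sizing:** "it is reasonable to assume the standard deviation of mean daily BG is bounded above by 45 mg/dl", followed by "Assuming the true BG difference between the treatment groups is zero, and using one-sided, two-sample t-tests, we require 78 subjects for each treatment group" for 80% power. No significance level is given.
- **Attrition:** "Accounting for 10% attrition rate, we would need 90 patients per treatment group, which means 180 subjects in total", for which the plan claims power above 80% in Aim 1.
- **Analysis:** the next paragraph turns to baseline characteristics and hypoglycemia rates, then says "Comparisons will be made with the use of Wilcoxon tests (or Kruskal-Wallis tests) and Chi-square tests (or Fisher's exact test) as appropriate". The one model it names is limited to secondary outcomes: "Multivariate linear regression will be conducted to assess the difference in continuous secondary outcomes between the two groups".

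The analysis paragraph mentions neither the 18 mg/dl margin nor a confidence limit. The hypothesis under Aim 1 expects glycemic control to be similar between the groups and does not say how similarity will be judged.

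**The concern.** A Wilcoxon, Kruskal-Wallis or ordinary t-test of no difference has a null hypothesis of zero difference. Rejecting it shows that the groups differ. Failing to reject it says nothing about whether CGM is worse by less than 18 mg/dl. The printed power belongs to a different test, one against the margin, and the analysis paragraph does not say that this test will be run.

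The primary efficacy conclusion on mean daily BG is at stake. With a hypothesis of similar control and no written rule, a non-significant P value could end up carrying the claim. The false-claim rate of such a reading is not controlled, and it rises as evaluable patients are lost. Without a stated alpha, the power of the proper test is not fixed either.

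**Working it through.** **Inputs, all from section IV unless marked**

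- Margin 18 mg/dl; SD 45 mg/dl (given as an upper bound); true difference 0 for power.
- One-sided two-sample t-test, 80% power, 78 per group.
- 10% attrition and 90 enrolled per group, so 90 × 0.9 = 81 evaluable.
- Alpha: not stated; solved for below.
- Two-sided 0.05 for the difference tests: my assumption.

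**Step 1. Reproduce the plan's figure.** Normal approximation: n per group = 2 × [SD × (z_alpha + z_power) / margin]².

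- One-sided 0.05: 2 × [45 × (1.645 + 0.842) / 18]² = 77.3, so 78. The exact noncentral-t calculation also gives 78 (power 80.0%).
- One-sided 0.025: 2 × [45 × (1.960 + 0.842) / 18]² = 98.1, so 99; exact t gives 100.

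Of these two conventional levels, only one-sided 0.05 gives the stated 78. For attrition, 78 / 0.9 = 86.7, so 87; the plan's 90 is a little more generous.

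**Step 2. Power of the margin test (exact t, SD 45, true difference 0)**

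| Evaluable per group | One-sided 0.05 | One-sided 0.025 |
|---|---|---|
| 78 | 80.0% | 69.9% |
| 81 | 81.3% | 71.6% |
| 90 | 84.8% | 76.1% |

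The claim of more than 80% holds at one-sided 0.05 and fails at one-sided 0.025.

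**Step 3. Compare the two criteria on the observed difference.** At 78 per group, SE = 45 × √(2/78) = 7.21 mg/dl, with 154 degrees of freedom.

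- Two-sided difference test: non-significant up to 1.975 × 7.21 = 14.2 mg/dl.
- Margin test at one-sided 0.05: passes only below 18 − 1.655 × 7.21 = 6.1 mg/dl.

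An observed CGM disadvantage between about 6.1 and 14.2 mg/dl would therefore be non-significant and still fail the margin.

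**Step 4. Illustration: CGM truly 18 mg/dl worse, and non-significance read as similarity.** The chance of a non-significant two-sided 0.05 result at SD 45 is below. The t-test is exact; the Wilcoxon figures come from simulation with normal data, 20,000 trials per cell.

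| Evaluable per group | t-test | Wilcoxon |
|---|---|---|
| 78 | 30.1% | 32.3% |
| 81 | 28.4% | 29.9% to 30.5% (two runs) |
| 90 | 23.9% | 25.5% to 25.9% (two runs) |

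The margin test at one-sided 0.05 passes in 5% of trials in this situation, by construction.

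**Step 5. Sensitivity of the illustration.** At 81 per group the t-test figure falls to 18.8% if the SD is 40, and to about 6% if the SD is 45 and CGM is truly 25 mg/dl worse. With skewed (lognormal) data of SD 45 and a true difference of 18, the Wilcoxon figure is 26.0%.

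**The case against.** The strongest reply is that the plan does name a non-inferiority test. Objective, margin, endpoint and one-sided t-test all stand under the same heading as the analysis paragraph, and a fair reader could take that t-test as the primary analysis. The Wilcoxon sentence comes straight after the one on hypoglycemia rates, is qualified to apply where appropriate, and includes a Kruskal-Wallis option that a two-arm comparison does not need. It reads like a generic list and never mentions mean daily BG.

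Much of this stands. The documents do not show that the sponsor intends to replace the margin test with a Wilcoxon test. But the t-test appears only as a sizing assumption, without an alpha or a success rule. If the Wilcoxon sentence concerns hypoglycemia only, then mean daily BG has no analysis stated beyond that assumption. Either reading leaves the same gap.

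A reader might also infer that the plan would call an inferior CGM arm similar about 30% of the time. The documents do not support this. Nowhere do they say that a non-significant P value will be read as similarity, and the similar control in Aim 1 is a hypothesis, not a decision rule. It is also tempting to raise the figure by taking 72 evaluable per group from the 80% completion rate in section IV. That rate covers the inpatient and ambulatory arms together; the Aim 1 sizing uses 10% attrition.

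Finally, a Wilcoxon test shifted by the margin, or a rank-based confidence interval, could address non-inferiority. The plan specifies neither.

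**Conclusion.** The concern holds as a gap in specification. The trial has a non-inferiority objective for mean daily BG and a sample size that fits it, but no stated alpha and no rule against the 18 mg/dl margin, and the tests listed in the analysis paragraph cannot show non-inferiority as named.

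The sample size itself is not wrong: it reproduces at one-sided 0.05. What the missing alpha leaves open is whether power with 81 evaluable per group is 81.3% or 71.6%.

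The 28–31% against 5% is a conditional illustration. It rests on a true difference exactly at the margin, the SD at its stated upper bound, 81 per group, an assumed two-sided 0.05, and a reading of non-significance that the plan neither adopts nor excludes. It shows why the rule should be written down; it is not an error rate of the plan.

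The margin and the power also cover only part of the primary efficacy question. Aim 1 and the list of primary outcomes name time in range, a percentage, to which a margin in mg/dl does not apply.

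**What to change.** In the analysis paragraph of section IV:

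1. State that the primary analysis of mean daily BG is the CGM minus POC mean difference with a one-sided 95% upper confidence limit, and that non-inferiority is declared only if that limit is below 18 mg/dl. This is the one-sided 0.05 level that reproduces 78 per group.
2. If a two-sided 95% interval is preferred, restate the power as about 72% with 81 evaluable per group; 80% would need about 100 evaluable per group.
3. Keep Wilcoxon and Chi-square tests for hypoglycemia and the other difference comparisons, and state that a non-significant difference test is not evidence of similarity.
4. State that the 18 mg/dl margin and the power above 80% apply to mean daily BG only, not to time in range.

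The cost is a few sentences. At one-sided 0.05 no extra patients or data are needed. The price is that a claim of comparable control must meet a stricter bar than a non-significant P value. The change does not supply a margin or a test for time in range; it only makes clear that the present sizing does not cover it.
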